ASD Parent Trainer: Online Coaching for Parents of Children With Autism NCT02469870

Study Protocol and Analysis Plan

3/2/17

Study Protocol and Analysis Plan

We employed a mixed-model repeated measures, randomized group design to evaluate the PR and TR programs, examining changes over time both within and across the programs, assessing whether there were improvements in each program. All research was conducted online. Participants were recruited nationally. Eligible parents had to (a) have access to necessary technology (i.e., computer with camera and microphone, high-speed Internet connection, and a mobile device with current operating system) and (b) speak English. Parents had to have at least one child who (a) had a medical diagnosis or special educational eligibility of ASD, (b) was between 3 – 8 years old, (c) lived in the home of the participating parent, and (d) engaged in challenging behavior that interfered with at least one family routine. Eligible participants completed informed consent online. Parents were assigned to either the PR or TR condition using block randomization.

Measures

To evaluate changes over time both within and between programs, we assessed family quality of life; parenting stress, behaviors, and knowledge; and child behavior (adaptive and maladaptive) using parent report measures. Additionally, at T3 we examined parents use of and satisfaction with the programs. The measures described in the following sections were used.

Quality of Life. The Family Quality of Life survey (FQOL; Summers et al., 2005) is a 25-item measure for families raising a child with intellectual or developmental disabilities. The measure includes domains of parenting, emotional well-being, physical/material well-being, and disability-related supports using a 5-point scale with responses ranging from (1) very dissatisfied to (5) very satisfied. In the current study we used the mean FQOL scores for analyses, which demonstrated excellent internal reliability (alpha = .91 at pretest).

Parenting Stress. The Parental Stress Scale (PSS; Berry & Jones, 1995) was developed to assess stress of parenting stress, and contains 18 items representing both positive and negative parenthood components. In the current study, it demonstrated strong internal reliability (alpha = .90 at all three time points), so all analyses used parents' mean scores.

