Participants were sent T1 approximately one week prior to accessing the Learning Management System (LMS), which housed both programs. Parents were notified to which group they were randomly assigned upon completion of T1. Participants were sent T2 six weeks after T1, and T3 was sent 4 weeks later. Honorarium checks in the amount of \$50 were mailed within four weeks of each survey completion. Participants who did not attend any PR sessions were not sent T2 or T3.

Program Descriptions

Both programs focused on ABA within the context of typical family routines. The content guided parents to identify target routines and behaviors of concern, learn about the patterns that may be affecting their children's behavior, and develop strategies to prevent problems, teach skills, and manage access to reinforcement. The LMS courses were divided into modules that included videos, written summaries of each video, fillable forms and other exercises to guide parents through activities to support the intervention process with their

children, and resource materials including links to relevant websites. The parents were expected to complete homework for each module. Parents were given access to the courses for the duration of the study and technical support was available.

Teaching Routines. Teaching Routines was entirely self-directed. The program included eight modules with videos for each ranging 3 – 5 minutes in duration. The topics were antecedent-behavior-consequence method, creating task analyses, antecedent-based strategies, communication, reinforcement, teaching methods, and overcoming obstacles. Participants were assigned six activities using fillable forms and provided additional resources including examples, a glossary of terms, and a list of websites. No feedback was given to the parents apart from the automated completion responses. The participants were given access to the TR LMS for the duration of the study, but post and follow-up assessments were completed at 6 and 10 weeks (i.e., same as the PR condition).

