Fidelity checks were conducted for 34% of the sessions. The fidelity checklist included items on content and parent participation. Fidelity for content ranged from 90-100% (M = 99%). Fidelity for participation ranged from 53-100% (M = 94%). Interrater reliability was conducted for 38% of sessions assessed by a second observer. Reliability was evaluated on an item-by-item basis, dividing the number of agreements by agreements plus disagreements and multiplying by 100 to obtain a percentage. Reliability was 87.5% for the content and 97.5% for participation. Dosage was measured as the percent of components (e.g., videos, forms, supplemental resources) accessed by the participants.

Data Analysis

Change was evaluated over time within condition using repeated-measures *t*-tests. To address hypotheses predicting differential change in outcome measures between condition over time we used analysis of covariance (ANCOVA) models that allow for examination of crosssectional effects and mean adjusted outcomes. The ANCOVA models (adjusted for baseline scores) were used for analyses of change in the outcome measures at posttest and follow-up.

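### The T3 comparison makes no use of T2 and no model estimates how the PR-TR difference changes between visits; a single repeated-measures model would do both

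*Combined protocol and SAP*

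**What the plan says.** The opening paragraph of the Study Protocol and Analysis Plan describes the study thus: "We employed a mixed-model repeated measures, randomized group design to evaluate the PR and TR programs". It gives the purpose as "examining changes over time both within and across the programs, assessing whether there were improvements in each program".

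Three surveys were planned. The last paragraph of Measures says "Participants were sent T2 six weeks after T1, and T3 was sent 4 weeks later", which puts T2 at week 6 and T3 at week 10. The same paragraph adds: "Participants who did not attend any PR sessions were not sent T2 or T3".

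The Data Analysis section is one paragraph. Within programs: "Change was evaluated over time within condition using repeated-measures" t-tests. Between programs, for hypotheses about differential change over time, it uses ANCOVA, described as "models that allow for examination of crosssectional effects and mean adjusted outcomes". The covariate and the time points come in the last sentence: "The ANCOVA models (adjusted for baseline scores) were used for analyses of change in the outcome measures at posttest and follow-up".

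The document gives no mixed model, program-by-visit term, covariance structure, analysis set or missing-data method.

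**The concern.** Three waves were collected to study change within and across programs, yet no specified between-program analysis uses T2 and T3 together. This has two consequences.

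1. An ANCOVA of T3 on program and T1 has no place for T2. Unless missing T3 values are imputed, and no imputation is mentioned, a parent with T1 and T2 but no T3 adds nothing to the T3 comparison. That loses precision. It can also bias the T3 effect if, beyond T1, the link between T2 response and failure to return T3 differs between programs. Such a difference is conceivable here: PR parents had educator contact and group meetings, while TR parents had only automated responses.
2. No estimate is given of whether a PR-TR difference at T2 is kept, grows or shrinks by T3. This gap exists even with full follow-up. A reader is left to compare two significance results, possibly from different sets of parents, which is not a valid test of change.

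**Working it through.** **No planned figure to reproduce.** The documents state no sample size, power, effect size, SD, correlation or loss rate. Every number below is an assumption or follows from one.

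**Assumed inputs.** 50 parents per arm; unit SD; correlations T1-T2 .65, T2-T3 .75, T1-T3 .60; T2 complete; nominal loss between T2 and T3 of 15%, 25% or 35%; where loss depends on T2, a log-odds slope of 1 per SD.

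**Estimators compared.**
- (a) Complete-case ANCOVA: regress T3 on arm and T1 in T3 respondents; the effect is the arm coefficient.
- (b) Joint model, in its maximum-likelihood form for loss after T2: regress T2 on arm and T1 in all parents (arm coefficient g); regress T3 on arm, T1 and T2 in T3 respondents (arm coefficient h, T2 coefficient k); the T3 effect is h + k·g.

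**Precision under random loss.** With loss fraction L, the large-sample variance ratio (a)/(b) is 1 / (1 − L·r²), where r is the partial T2-T3 correlation given T1.
- r = (.75 − .65 × .60) / √[(1 − .65²)(1 − .60²)] = .36 / √(.5775 × .64) = .592, so r² = .351.
- L = .15: 1 / (1 − .0526) = 1.06.
- L = .25: 1 / (1 − .0877) = 1.10.
- L = .35: 1 / (1 − .1227) = 1.14.

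Simulation (4000 trials per scenario) gave 1.05, 1.10 and 1.12. The range is therefore about 5% to 14% in variance, or about 2% to 7% in standard error (√1.05 = 1.02, √1.14 = 1.07).

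**Why bias depends on the arms differing.** The bias of (a) is approximately k × (shift in PR − shift in TR). Each shift is the mean T2 residual, given T1, among parents who return T3. Here k = .36 / .5775 = .62. If selection on T2 is alike in both arms, the two shifts nearly cancel.

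**Simulated bias of (a), no true effect, nominal loss 15/25/35%:**

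| T3 loss depends on T2 | Bias (SD) | Type I error |
|---|---|---|
| alike in both arms | 0.001 / 0.004 / 0.000 | 4.9 / 5.1 / 4.6% |
| in one arm only | 0.053 / 0.090 / 0.114 | 5.8 / 7.7 / 8.6% |
| in opposite directions | 0.112 / 0.180 / 0.232 | 10.0 / 16.2 / 20.8% |

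Repeat runs gave 0.06 to 0.12 SD for one arm and 0.12 to 0.24 SD for opposite directions. With a true effect of 0.4 SD and dependence alike in both arms, the bias was −0.01 to −0.02 SD, toward no effect. Under no true effect the joint model stayed within about 0.005 SD of zero, with error of 4.5% to 5.2%.

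**Second set of assumptions.** True effect 0.40 SD; correlations, in the same order, .6/.7/.5 or .7/.8/.6; base loss 10% to 30%. Bias of (a) was about nil when loss was random or depended on T1 only, −0.01 to −0.02 SD when T2-dependence was alike in both arms, 0.04 to 0.09 SD for PR only, and 0.08 to 0.21 SD for opposite directions. Variance was about 0% to 17% larger than for (b), whose estimates stayed at 0.39 to 0.41.

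**The case against.** The strongest reply is that ANCOVA adjusted for baseline is a standard, valid test of differential change from baseline, so preferring a mixed model is a matter of efficiency. Loss between T2 and T3 is never reported and may be small, since each completed survey carried a $50 payment. With negligible loss, both the bias and the precision gain disappear. No stated hypothesis compares the T2 effect with the T3 effect. The document is also written in the past tense, so a new model would be a later re-analysis. All of this stands, and it limits the weight of the point.

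Four stronger readings are tempting, and the documents do not support them.
- **That the plan contradicts itself.** The mixed-model wording describes the design and may mean only a between/within-subject layout. It is an unclear label, not a broken promise of a particular analysis.
- **That the plan prescribes a respondents-only analysis.** It does not say so. That, and a separate model per visit, is the usual reading of ANCOVA with no missing-data method given.
- **That T2 data are thrown away.** They still enter the T2 ANCOVA and the T1-T2 t-test. Only the T3 comparison lacks them.
- **That poor responders dropping out is enough to bias T3 and inflate false positives.** Alike in both arms, it does neither to a material degree.

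What the reply does not answer is that the hypotheses concern differential change between conditions over time. No specified model estimates a program-by-visit effect, and the T3 comparison leaves relevant collected data unused.

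**Conclusion.** The point holds as an inexpensive improvement to the analysis, not as proof of a biased result. It is certain that no between-program model combining T2 and T3 is specified and that no missing-data method is given. The cost depends on the complete-case reading and on the assumed inputs:
- about 5% to 14% more T3 variance under random loss;
- bias of at most about 0.02 SD, with type I error near 5%, if T3 loss depends on T2 alike in both arms;
- bias of about 0.05 to 0.12 SD if it does so in one arm only, and 0.11 to 0.24 SD in opposite directions, which is an extreme case that nothing in the documents suggests.

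The actual loss after T2 is unknown, so the size in this trial is unknown. A reader might also infer that a mixed model would repair the missing data that the plan does describe. It would not: PR parents who attended no session have neither T2 nor T3, so there is no T2 score from which to recover information.

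**What to change.** For each outcome, fit one baseline-adjusted repeated-measures mixed model:
- responses: T2 and T3;
- fixed effects: program, visit, program-by-visit, T1 score and T1-by-visit;
- covariance: unstructured within parent;
- estimation: REML with Kenward-Roger degrees of freedom;
- analysis set: all randomised parents with any post-baseline data.

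Report the PR-TR contrast at T2, at T3, and the difference between the two. Keep the per-visit ANCOVAs as a sensitivity analysis, and state their analysis set and how missing scores were handled. Report loss between T2 and T3 by arm, so that a reader can judge which of the scenarios above is relevant. As the document is retrospective, label the new model as added later.

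The cost is a rewritten Data Analysis paragraph and one re-run on data already held. The model relies on data missing at random given T1, T2 and program, which is weaker than what the complete-case T3 ANCOVA needs, and it adds a few covariance parameters. The PR parents who were sent no follow-up survey remain a separate problem.
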